21.1 Paper Size, Orientation and Margins

The margin, page size and line size specifications as stipulated in Table 23.1 will be used for the presentation of all TLFs.

Table 23.1: Output margin, page size and line size specifications

	Landscape	Portrait
Margins (Inches):		
Top	1.25	1
Bottom	1.25	1
Left	0.87	1.25
Right	0.87	1
Header (Inches)	0.5	0.5
Footer (Inches)	0.5	0.5
SAS® specifications:		
PAGESIZE	46	67
LINE SIZE	134	93

21.2 Fonts

The font type “Courier New” should be used as default for tables and data listings, with a font size of 10. The font color should be black. No bolding, underlining and italics are permitted.

Figures should have a default font of “Times Roman,” “Helvetica” or “Courier New.”

21.3 Header Information

Headers should be defined as follows:

- The header should be placed at the top of the page (same place on each page).
- The sponsor's name should appear in row 1, left-aligned.
- The word “CONFIDENTIAL” should appear in row 1, right aligned.
- The protocol number should appear in row 2, left-aligned.
- The page identification in the format Page X of Y (where Y is the total number of pages for the TLF) should appear in row 2, right aligned.
- The TLF identification number should appear in row 3, centered.
- The TLF title should start in row 4, centered.

- The TLF population should appear in row 5, centered. The population should be spelled out in full, e.g., *Safety analysis population* in preference to *Safety analysis population*.
- Row 6 should be a continuous row of underscores ('_') (the number of underscores should equal the line size).
- Row 7 should be a blank line.
- Mixed case should be used for titles.
- Titles should not contain quotation marks or footnote references.
- The column headings should be underlined with a row of underscores ('_').
- Column headings spanning more than one column should be underlined and have underscores on either side of the title and should be centered.
- Column headings containing numbers should be centered.
- Column headings should be in mixed case.
- In general, the analysis population count should appear in the column header in the form "(N=XX)."

21.4 Table and Data Listing Table, Listing and Figure (TLF) Conventions

21.4.1 General

- The first row in the body of the table or data listing should be blank.
- The left-hand column should start in Column 1. No indenting or centering of the TLF should occur.
- Rounding should be done with the SAS® function ROUND.
- Numerical values in tables should be rounded, not truncated.
- Numerical values should be decimal point aligned.
- Text values should be left aligned.
- The first letter of a text entry should be capitalized.
- The study drug should appear first in tables with treatment group as columns.
- All variables contained on the eCRF (which have data present) should appear in the data listings, along with all derived data appearing in the corresponding tables.
- The width of the TLF should match the line size.

21.4.2 Univariate statistics

- Statistics should be presented in the same order across tables (i.e., n, mean, SD, minimum, median and maximum).

- If the original data has N decimal places, then the summary statistics should have the following decimal places:
 - Minimum and maximum = N
 - Mean and Percentiles (e.g., median, Q1 and Q3) =N + 1.
 - SD = N + 2.

21.4.3 Frequencies and percentages [n, (m) and %]

Percent values should be reported inside parentheses with percent symbol, no blank spaces are included within the parentheses, e.g., "(25%)." percentages greater than 0 and less than 1 as "<1%" and those greater than 99 and less than 100 as ">99%". Percentages exactly equal to 0% will be shown as blanks in the table. So, counts of 0 will be presented as 0 and not as 0 (0%).

21.4.4 Confidence intervals (CIs)

- CIs should be presented with one additional decimal place as that of the raw data, and SDs and standard errors (SEs) with two additional decimal places as that of the raw data.
- Confidence intervals are displayed within round brackets and separated by a comma. The lower limit is presented first, and the upper limit is presented second. The confidence interval is placed either beside or below the corresponding estimate. The estimate and the confidence limits are presented using the same degree of precision.

21.4.5 P-values

The precision of calculated p-values is expressed to one more decimal place than the precision of the significance criteria. For example, if the significance threshold is 0.05, the calculated p-values are expressed to three decimal places; if the significance threshold is 0.025, the calculated p-values are expressed to four decimal places. If the p-value is smaller than can be represented in this number of decimal places, use a "<" with the smallest printable value (e.g. when presenting p-values to three decimal places and a calculated p-value is less than 0.001, it is reported as "<0.001," rather than "0.000"). Avoid rounding p-values to the nearest decimal place. Instead use the most conservative value (e.g. ceiling) based on the test being performed.

21.4.6 Ratios

- Ratios should be reported with one additional decimal place as that of the raw data.

21.4.7 Spacing

- There should be a minimum of 1 blank space between columns (preferably 2).

21.4.8 Missing values

- A "0" should be used to indicate a zero frequency.

- A blank will be used to indicate missing data in data listings.

21.5 Figure output conventions

Figures should be provided in RTF files using the SAS® Output Delivery System (ODS).

21.6 Dates and times

Depending on data available, dates and times will take the form ddMMMyyyy and hh: mm.

21.7 Spelling format

The spelling format to be used is English US.

21.8 Presentation of treatment group

FF/UMEC/VI

21.9 Presentation of visits

- Pre-screen (Visit 0)
- Screen (Visit 1)
- Visit 2
- Visit 3
- Telephonic (Visit 4)
- Visit 5
- Safety follow-up (Visit 6)

22. Appendix 2: Partial date conventions and Concomitant medication guidelines

The whole missing date will not be imputed for this study; only partial date imputation will be performed. Conventions pertaining to partial dates are presented.

Table: Algorithm for partial date imputation

Element	Reporting Detail									
General	
 Partial dates will be displayed as captured in participant listing displays. However, where necessary, display macros may impute dates as temporary variables for sorting data in listings only. In addition, partial dates may be imputed for 'slotting' data to study phases or for specific analysis purposes as outlined below. Imputed partial dates will not be used to derive study day, time to onset or duration (e.g., time to onset or duration of adverse events), or elapsed time variables (e.g., time since diagnosis). In addition, imputed dates are not used for deriving the last contact date in overall survival analysis dataset. 									
Adverse Events	
 Partial dates for AE recorded in the CRF will be imputed using the following conventions: 
 
 Missing start day	 
 If study intervention start date is missing (i.e. participant did not start study intervention), then set start date = 1st of month. 	
 
 	 
 Else if study intervention start date is not missing: 
 If month and year of start date = month and year of study intervention start date, then 
 If stop date contains a full date and stop date is earlier than study intervention start date, then set start date= 1st of month. Else set start date = study intervention start date. 	
 
 Missing start day and month	 
 If study intervention start date is missing (i.e. participant did not start study intervention), then set start date = January 1. 	
 
 	 
 Else if study intervention start date is not missing: 
 If year of start date = year of study intervention start date, then 	
 
		Missing start day	
 If study intervention start date is missing (i.e. participant did not start study intervention), then set start date = 1st of month. 		
 Else if study intervention start date is not missing: 
 If month and year of start date = month and year of study intervention start date, then 
 If stop date contains a full date and stop date is earlier than study intervention start date, then set start date= 1st of month. Else set start date = study intervention start date. 	Missing start day and month	
 If study intervention start date is missing (i.e. participant did not start study intervention), then set start date = January 1. 		
 Else if study intervention start date is not missing: 
 If year of start date = year of study intervention start date, then
Missing start day	
 If study intervention start date is missing (i.e. participant did not start study intervention), then set start date = 1st of month. 									
	
 Else if study intervention start date is not missing: 
 If month and year of start date = month and year of study intervention start date, then 
 If stop date contains a full date and stop date is earlier than study intervention start date, then set start date= 1st of month. Else set start date = study intervention start date. 									
Missing start day and month	
 If study intervention start date is missing (i.e. participant did not start study intervention), then set start date = January 1. 									
	
 Else if study intervention start date is not missing: 
 If year of start date = year of study intervention start date, then 									

Element	Reporting Detail						
	
 – If stop date contains a full date and stop date is earlier than study intervention start date, then set start date = January 1. – Else set start date = study intervention start date. 
Else set start date = January 1.
 
 
 Missing end day	A '28/29/30/31' will be used for the day (dependent on the month and year).	
 
 Missing end day and month	No Imputation	
 
 Completely missing start/end date	No imputation	
 
	Missing end day	A '28/29/30/31' will be used for the day (dependent on the month and year).	Missing end day and month	No Imputation	Completely missing start/end date	No imputation
Missing end day	A '28/29/30/31' will be used for the day (dependent on the month and year).						
Missing end day and month	No Imputation						
Completely missing start/end date	No imputation						
Concomitant Medications	
 • Partial dates for any concomitant medications recorded in the CRF will be imputed using the following convention: 
 
 Missing start day	 
If study intervention start date is missing (i.e. participant did not start study intervention), then set start date = 1st of month.
 
Else if study intervention start date is not missing:
 
 • If month and year of start date = month and year of study intervention start date, then 
 – If stop date contains a full date and stop date is earlier than study intervention start date, then set start date= 1st of month. – Else set start date = study intervention start date. 
Else set start date = 1st of month.
 	
 
	Missing start day	
If study intervention start date is missing (i.e. participant did not start study intervention), then set start date = 1st of month.
 
Else if study intervention start date is not missing:
 
 • If month and year of start date = month and year of study intervention start date, then 
 – If stop date contains a full date and stop date is earlier than study intervention start date, then set start date= 1st of month. – Else set start date = study intervention start date. 
Else set start date = 1st of month.
				
Missing start day	
If study intervention start date is missing (i.e. participant did not start study intervention), then set start date = 1st of month.
 
Else if study intervention start date is not missing:
 
 • If month and year of start date = month and year of study intervention start date, then 
 – If stop date contains a full date and stop date is earlier than study intervention start date, then set start date= 1st of month. – Else set start date = study intervention start date. 
Else set start date = 1st of month.
						
	
 
 Missing start day and month	 
If study intervention start date is missing (i.e. participant did not start study intervention), then set start date = January 1.
 
Else if study intervention start date is not missing:
 
 • If year of start date = year of study intervention start date, then 
 – If stop date contains a full date and stop date is earlier than study intervention start date, then set start date = January 1. 	
 
	Missing start day and month	
If study intervention start date is missing (i.e. participant did not start study intervention), then set start date = January 1.
 
Else if study intervention start date is not missing:
 
 • If year of start date = year of study intervention start date, then 
 – If stop date contains a full date and stop date is earlier than study intervention start date, then set start date = January 1. 				
Missing start day and month	
If study intervention start date is missing (i.e. participant did not start study intervention), then set start date = January 1.
 
Else if study intervention start date is not missing:
 
 • If year of start date = year of study intervention start date, then 
 – If stop date contains a full date and stop date is earlier than study intervention start date, then set start date = January 1. 						

Element	Reporting Detail	
		
 – Else set start date = study. intervention start date. 
Else set start date = January 1.

	Missing end day	A '28/29/30/31' will be used for the day (dependent on the month and year).
	Missing end day and month	A '31' will be used for the day and 'Dec' will be used for the month.
	Completely missing start/end date	No imputation
Age	
 • Age will be calculated based on the Pre-Screening Visit date (or Screening if pre-screening not performed). • Only year of birth is collected on eCRF. Day and Month of birth are imputed as 30 June. Age is derived using the date of the screening visit. • All participants with imputed age of 39 or 40 years will be source data verified, and presence/ absence of protocol deviation on the inclusion criteria #1 will be taken into consideration in the derivation for the analysis variable age. 
Birth date will be presented in listings as 'YYYY'.

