5.3 Intended-to-Treat population (ITT)

This analysis population will include all participants who received at least one dose of study treatment.

6. General considerations

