7.2 Missing data

For efficacy data, missing values will be assumed to be missing at random (MAR) & no imputation will be performed.

For adverse event, prior and concomitant medication data, partial date imputations will be performed where at least the year is provided.

8. Output presentations

The templates provided in the separate output templates document describe the format and content for presentation of tables, listings, and figures (TLFs).

For continuous measures, summary statistics will include number of participants (n), mean, standard deviation (SD), median, minimum, and maximum for both the actual and the change from baseline measurements. For categorical measures, summary statistics will include number of participants (n), frequency, and percentages.

All percentages (%) for a specific summary are calculated using the total number of participants included in the relevant analysis population as the denominator, unless otherwise specified.

9. Participant disposition and withdrawal

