14.1 Variables and derivations

Adverse Events (AEs) will be coded using standard GSK dictionary, MedDRA central coding dictionary, version 26.0 or higher.

For the definition of Adverse events (AE) and Serious adverse event (SAE) refer to the protocol section 10.6.

The following parameters will be summarised for the participant's adverse events as mentioned in eCRF:

- Number of participants with at least one AEs pre treatment
- Number of participants with at least one AE during treatment
- Number of participants with at least one AE post treatment
- Number of participants with at least one Drug related AE.
- Number of participants with at least one serious AEs
- Number of participants with at least one Drug related serious AEs
- Number of participants with at least one AESI
- All Adverse Events
- Ongoing AEs
- AEs by Severity
- AEs by Outcome
- AEs by Action Taken with Study treatment
- AEs leading to Death

Derivations:

- The question "Adverse event related to study treatment" is answered "Yes," then respective AEs will be considered as treatment related AE.
- The question "Is the adverse event serious" is answered as "Yes" then respective AE will be considered as serious AEs.
- The question "Is the adverse event serious" is answered as "Yes" and the question "Adverse event related to study treatment" is answered "Yes," then respective AEs will be considered as treatment related SAEs.
- If seriousness criteria are "DEATH" and outcome of adverse event is "FATAL" then we will consider it as AE leading to death.
- Participant's primary reason for discontinuation captured in the eCRF page, study treatment discontinuation is "ADVERSE EVENT" then we will consider it as AE leading to early withdrawal from study.
- Pre- Treatment AEs: AE Start Date < Study Treatment Start Date
- Post- Treatment AE's: AE Start Date > Study Treatment Stop Date

- During Treatment AE's: Treatment Start Date \leq AE Start Date \geq Treatment Stop Date

In section 22 Appendix 2 the algorithm is given for calculation of partial date imputation for Adverse Events, and it will be used for partially missing AE, start and end date imputation.

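### As printed, the SAP rule for an AE with a missing start day covers only the month of first dose, so such an AE in any other month gets no date and no treatment phase

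*SAP*

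**What the plan says.** SAP 7.2 sets the general rule for AE and medication dates: "partial date imputations will be performed where at least the year is provided". SAP 14.1 sends partly missing AE dates to Appendix 2 (Section 22), whose general paragraph allows imputation for placing events in study phases.

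For an AE with a missing start day, Appendix 2 gives two branches:

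- No first-dose date: "If study intervention start date is missing (i.e. participant did not start study intervention), then set start date = 1st of month".
- First-dose date present: "If month and year of start date = month and year of study intervention start date, then". Inside that condition, the date is the 1st of the month if a full stop date precedes first dose. Otherwise: "Else set start date = study intervention start date".

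The row ends there. The AE row for a missing day and month closes with "Else set start date = January 1". The concomitant-medication row for a missing start day closes with "Else set start date = 1st of month".

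SAP 14.1 then defines pre-, during- and post-treatment AEs by comparing the AE start date with the treatment dates, for example "Pre- Treatment AEs: AE Start Date < Study Treatment Start Date". SAP 17.1 makes the primary estimand while-on-treatment.

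**The concern.** The AE tables use the ITT set, defined in SAP 5.3: "This analysis population will include all participants who received at least one dose of study treatment". Everyone in it has taken a dose, so the branch for participants with no first-dose date does not serve these tables. Only the first-dose-month branch is left, and it gives nothing for an AE recorded in an earlier or later month.

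The primary summary depends on phase. An AE, SAE or AESI with no start date meets no during-treatment comparison, although its month and year are known and often settle the matter. The programmer would have to invent a rule for the primary endpoint or leave the event out.

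**Working it through.** There is no stated figure to reproduce; the check is of the decision logic and then of its reach.

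**1. The rows side by side, for a dosed participant**

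| Row in Appendix 2 | Same month (or year) as first dose | Any other month (or year) |
|---|---|---|
| AE, day missing | 1st of month or first-dose date | nothing printed |
| AE, day and month missing | 1 January or first-dose date | 1 January |
| Concomitant medication, day missing | 1st of month or first-dose date | 1st of month |

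The last line of the AE day-missing row belongs to the inner test on the stop date. Attached to the outer test, it would move an AE recorded in September back to a July first dose, against its own recorded month. The result also runs against the information available: a year-only AE date always gets an imputed start, while a month-and-year date in a later month gets none. Where Appendix 2 intends no imputation it says so, as for a missing AE end day and month. This row does not.

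**2. Worked example.** First dose 15 July, last dose on Day 84, which is 6 October (17 + 31 + 30 + 6 = 84 days).

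| AE month, day missing | As printed | With 1st of month added |
|---|---|---|
| June | no date | 1 June, before treatment |
| July | 15 July, on treatment | 15 July, on treatment |
| August | no date | 1 August, on treatment |
| September | no date | 1 September, on treatment |
| October | no date | 1 October, on treatment |

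The on-treatment entries use the evident intent of the during-treatment rule: start date from first to last dose inclusive.

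**3. Share of treatment time outside the first-dose month.** Inputs: 84 treatment days (Protocol 1.1, last dose on Day 84); first-dose dates assumed uniform over 365 days; full course taken. With first dose on day s of a month of length L, the first-dose month holds (L − s + 1)/84 of the course.

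- Summed over a year, L − s + 1 gives 7 × 496 + 4 × 465 + 406 = 5,738 days. The mean is 5,738/365 = 15.72 days, and 15.72/84 = 18.7%.
- Share outside the first-dose month: 100% − 18.7% = 81.3%.
- Extremes: first dose on the 1st of a 31-day month gives 1 − 31/84 = 63.1%. First dose on the last day of a month gives 1 − 1/84 = 98.8%.
- Enumerating all 365 start dates splits the 81.3% into 62.6% in months wholly between the first-dose and stop months and 18.7% in the stop month.

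**4. Does the added branch work?** The 1st of any later month up to the stop month falls after first dose and not after last dose. Enumeration confirmed this for all 365 start dates.

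**5. A dependency.** SAP 14.1 prints the second half of the during-treatment rule as AE start date at or after treatment stop date. Read as printed, 1 August in the example is before 6 October and fails. The branch therefore helps only once that inequality is corrected.

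**The case against.** **A line may have been lost in reading the PDF.** The AE table is visibly broken in the text reviewed, and the closing branches that survive elsewhere are trailing lines of the kind that could drop out. The row appears twice without the branch, but both copies come from one page, so this is not independent confirmation. The objection stands to this extent: the row must be checked against the source file.

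**The intent is clear from SAP 7.2 and the neighbouring rows.** True, and it makes this a drafting slip. The rule as printed still gives no date.

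**Month and year often suffice.** For a month wholly between first and last dose, the order is known without a day; those months hold about 62.6% of treatment days. A careful programmer could place such an event, but no SAP rule says to do so. Only the stop month is truly ambiguous.

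**The effect on results is limited.** The supplementary estimand is meant to report all AEs regardless of discontinuation, and listings show partial dates as captured. The primary measure counts participants, so the overall any-AE percentage moves only if a participant has no other AE counted on treatment. Rows by system organ class and preferred term could move more readily.

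Three stronger readings are tempting, and the documents do not support them:

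- *The events would be counted as pre-treatment, because SAS sorts a missing value below any date.* SAP 6.5 names SAS, but nothing says a missing date is compared without a check. Protocol 8.3.1 records most pre-dose occurrences as medical history, so such a count would also be conspicuous.
- *Four in five AEs with a missing day would be lost.* The 81% is a share of days. It becomes a share of AEs only if onsets and missing days are spread evenly over treatment, which the documents do not say.
- *Missing days are likely because Day 85 looks back over 85 − 28 = 57 days.* Participants keep a Medical Problems worksheet that is reviewed at visits (Protocol 8.2.2, 8.3.2), and SAEs are to be reported within 24 hours. The documents give no rate of missing days.

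**Conclusion.** The point holds as a minor defect. As printed, the AE missing-start-day row gives a dosed participant a date only in the first-dose month, contrary to SAP 7.2 and out of line with its sibling rows. A partly dated AE in another month has no phase under SAP 14.1 and can be left out of the while-on-treatment primary summary.

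The months without a rule hold on average 81% of treatment days (63% to 99%), assuming uniform start dates and a full 84-day course. The number of AEs affected is unknown and could be zero. The conclusion rests on the row as read from the PDF being complete.

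**What to change.** 1. Check the AE missing-start-day row against the source file of the SAP.
2. If the branch is absent, add the line already used for concomitant medication, "Else set start date = 1st of month", at the outer level of that row.
3. Correct the during-treatment rule in SAP 14.1 to Treatment Start Date ≤ AE Start Date ≤ Treatment Stop Date. Without this the imputed dates do not classify as on treatment.

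The cost is one line in Appendix 2, one inequality in SAP 14.1, and the matching lines of code. The downside is that an AE in the month of last dose counts as on treatment even if it began just after the last dose. For a safety endpoint that is conservative, and it can be stated in a table footnote.

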5.1. Inclusion Criteria

Participants eligible for enrolment in the study must meet all of the following criteria:

1. **Informed Consent:** A signed and dated written informed consent prior to study participation.
2. **Type of participant:** Outpatient.
3. **Age:** Participants 40 years of age or older at Screening (Visit 1).
4. **Gender:** Male or female participants.

Female participants:

A female participant is eligible to participate if she is not pregnant, not breastfeeding, and at least one of the following conditions applies:

- Not a woman of childbearing potential (WOCBP)

OR

- A WOCBP who agrees to follow the contraceptive guidance in [Appendix 2](#) during the treatment period and until the safety follow-up contact after the last dose of study intervention.

5. **COPD Diagnosis:** An established clinical history of COPD in accordance with the definition by the American Thoracic Society/European Respiratory Society [[Celli, 2004](#)].
6. **Smoking History:** Current or former cigarette smokers with a history of cigarette smoking of ≥ 10 pack-years at Screening (Visit 1) [number of pack years = (number of cigarettes per day / 20) x number of years smoked (e.g., 20 cigarettes per day for 10 years, or 10 cigarettes per day for 20 years)]. Previous smokers are defined as those who have stopped smoking for at least 6 months prior to Visit 1. *Note: Pipe and/or cigar use cannot be used to calculate pack-year history.*
7. Patient with history of ≥ 2 moderate exacerbations or one severe (hospitalized) exacerbation in the previous 12 months, and with a score of ≥ 10 on the CAT eligible for the study treatment in the opinion of the investigator and documented post salbutamol FEV1/FVC ratio of <0.70
8. **Existing COPD maintenance treatment:** Participant must be receiving daily long-acting maintenance treatment for their COPD for at least 3 months prior to Screening. To be eligible for the study treatment phase, participants must be compliant with their

existing COPD maintenance therapy (in the opinion of the investigator) for the preceding two weeks prior to screening.

Note: Participants receiving only short-acting COPD medications are not eligible.

9. A negative test for **active COVID-19** at Visit 1. The test should be done using a molecular (PCR or antigen test) approved by the country regulatory authorities.

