3.1 Design overview

This is a phase IV, 12-week, single arm, multi-centre study evaluating single inhaler triple therapy (FF/UMECH/VI) once daily via the ELLIPTA inhaler.

Figure 4.1.1 Study Design Schema

*At day 84 (telephonic visit), participant will be instructed by the investigator telephonically to take the morning dose of study treatment/COPD medication, between 8am and 11am.

Approximately 306 participants will be screened to enrolled 229 (assuming 25% screen failure) to the study treatment phase for achieving 220 evaluable participants at the end of the study (assuming 4% withdrawal from study treatment).

At the start of the treatment period, participants will discontinue all existing COPD medications but may continue their study-supplied rescue salbutamol on an as-needed basis (rescue medication) throughout the study.

Clinic Visits will occur at Pre-Screening (Visit 0), Screening (Visit 1), Start of Treatment (Day 1, Visit 2), Day 28 (Visit 3), and Day 85 (Visit 5). Day 84 (Telephonic Visit 4) and Safety follow-up (Visit 6) conducted 1 week after completing the 12-week treatment period will be a telephone contact. Participants will sign an informed consent form (ICF) at a Pre-Screen or Screening Visit and will be assigned a participant identifier. Note: Visit 0 and Screening (Visit 1) may occur on the same day based on discretion of the study participant and discretion of Investigator.

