13.1 Variables and derivations

All medications will be coded using the WHO-DD, dated March, 1, 2023 or higher.

Prior medications are defined as any medication taken prior to first administration of the study treatment.

'Concomitant medications' are defined as any medication taken after or on the day of first administration of the study treatment.

In section 22 Appendix 2 the algorithm is given for calculation of partial date imputation for prior and concomitant medications, and it will be used for partially missing prior and concomitant medications, start and end date imputation.

The following parameters will be summarised as prior and concomitant medications separately:

- Number of participants with at least one prior and concomitant medication
- Number of participants for each prior and concomitant medication by ATC and PT.

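### For medications with a year-only start in the dosing year, the SAP's imputation rule can place the start after the stop, or remove pre-dose use that inclusion criterion 8 requires

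*SAP*

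**What the plan says.** SAP Appendix 2 (section 22) gives the rule in its concomitant-medication rows. For a start with day and month missing, in a participant who was dosed, it first asks whether the year matches: "If year of start date = year of study intervention start date, then" a test on the stop date applies: "If stop date contains a full date and stop date is earlier than study intervention start date, then set start date = January 1". If the test fails, the default is "Else set start date = study. intervention start date". If the year does not match, the start is January 1.

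Stops are imputed separately. A stop with only the day missing goes to the last day of its month. For a stop with day and month missing, "A '31' will be used for the day and 'Dec' will be used for the month". The start rule does not look at these imputed stops.

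SAP 13.1 applies the algorithm to both prior and concomitant medications. It states: "Prior medications are defined as any medication taken prior to first administration of the study treatment". Concomitant means taken on or after the day of first dose. The general row of Appendix 2 allows imputed dates for assigning data to study phases, but not for durations or time to onset.

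Two design facts bear on the rule. Protocol 5.1, criterion 8: "Participant must be receiving daily long-acting maintenance treatment for their COPD for at least 3 months prior to Screening". SAP 3.1: at the start of the treatment period "participants will discontinue all existing COPD medications".

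**The concern.** The stop-date test has two gaps. It ignores partial stops, even when the recorded month is plainly before dosing. It is also strict, so a complete stop on Day 1 fails it. In both cases the start moves to Day 1.

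The first gap can produce an impossible date order. The second can give a participant's existing maintenance therapy a start that eligibility rules out, because that therapy must have been in use for months. At stake is the prior-medication summary (SAP 13.2). Protocol 6.8 has COPD medications from the 3 months before screening recorded, and this table is where they would be expected to appear.

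**Working it through.** No figure in the plan depends on this rule, so there is nothing to reproduce. The check applies the rule literally to constructed records. Day 1 = 15 Aug 2023 is an assumption for illustration.

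**Rule.** If the start year equals the Day 1 year: start = 1 January if the stop is complete and stop < Day 1; otherwise start = Day 1. If the start year is earlier: start = 1 January of that year.

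| Recorded start | Recorded stop | Stop test | Imputed start | Imputed stop | Result |
|---|---|---|---|---|---|
| 2023 | 14 Aug 2023 | met | 1 Jan 2023 | 14 Aug 2023 (as recorded) | correct, prior |
| 2023 | Jun 2023 | fails, not complete | 15 Aug 2023 | 30 Jun 2023 | start after stop |
| 2023 | 15 Aug 2023 | fails, not earlier | 15 Aug 2023 | 15 Aug 2023 (as recorded) | no pre-dose use |
| 2023 | Aug 2023 | fails, not complete | 15 Aug 2023 | 31 Aug 2023 | no pre-dose use |
| 2023 | 2023 | fails, not complete | 15 Aug 2023 | 31 Dec 2023 | no pre-dose use |
| 2022 | Jun 2023 | not reached | 1 Jan 2022 | 30 Jun 2023 | correct, prior |

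**Size of the inversion in the second row.** From 30 Jun to 15 Aug is 31 (July) + 15 (August) = 46 days.

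**How general it is.** All pairs of start and stop days from 1 January to the day before dosing were enumerated for four assumed Day 1 dates, with the start recorded as year only:

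- Complete stop: 0% are moved to Day 1.
- Month-year stop: 100% are moved to Day 1. The share with start after stop is 75% (Day 1 = 15 April), 86% (15 July), 89% (15 September) and 92% (15 December).
- Year-only stop: 100% are moved to Day 1 and none invert, because the stop goes to 31 December.

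These shares treat all pairs as equally likely. They describe the rule and do not predict the data.

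**When qualifying therapy is exposed.** It must have started in the dosing year and at least 3 months before Screening. The earliest such start is 1 January, giving Screening about 1 April and Day 1 about 2 April. So Day 1 must fall in about April or later. Enrolment dates are not given. The protocol amendment on which the SAP rests is dated 03 May 2023 (SAP 1.1), so anyone enrolled under it in 2023 meets that condition.

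**Does comparing the imputed stop repair it?** For stop Jun 2023, 30 Jun < 15 Aug, so the start becomes 1 Jan 2023 and the order is valid. For stops of 15 Aug 2023, Aug 2023 and 2023, the stop used is 15 Aug, 31 Aug and 31 Dec. None is earlier than Day 1, so the start stays on Day 1. Those records need a second rule.

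**The case against.** The strongest reply is that this is a narrow edge case in a descriptive table. Much of that stands. Earlier-year starts are handled correctly. A complete stop on the day before dosing is also handled correctly, and such a stop is plausible because existing therapy ends as treatment begins. Sending ambiguous records to the treatment period is a cautious default that avoids missing on-treatment use, and for an ongoing record of unknown start it is defensible. Listings show partial dates as captured, so the original entry stays visible.

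Three stronger readings are tempting, and the documents do not support them:

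- A reader might infer that every affected record is certainly put in the wrong table. SAP 13.1 does not say which date decides. The inverted record has an imputed stop before Day 1 and could still be classed as prior by its stop.
- A reader might multiply an assumed share of regimens begun in the dosing year by an assumed share with unknown month to count the participants affected. The documents give neither share, and the product would still omit the stop-date condition.
- A reader might infer that finished corticosteroid or antibiotic courses will pass for prohibited medication. That needs a course with a known end month and an unknown start month. Prohibited use is reported through the protocol-deviation summary (Protocol 9.3.1), and nothing says deviations are derived from imputed dates.

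What the reply does not remove is that the rule, as written, yields impossible date order for some records and contradicts an eligibility criterion for others.

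**Conclusion.** The point holds in a limited form. For year-only medication starts in the dosing year, the rule gives a start after the stop when the stop is a month and year before the dosing month. It gives existing maintenance therapy no pre-dose use when the stop is on Day 1 or is recorded only as the dosing month or year. In that second case the therapy drops out of the prior-medication table if classification is by start date, which is an assumption because the SAP names no deciding date.

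The number of records is unknown. The effect is confined to the descriptive prior and concomitant medication tables. A reader might infer an effect on the efficacy result, since FEV1 change is measured from a baseline on background therapy. However, the MMRM in SAP 18.1.2 has no medication term, and neither the FEV1 nor the primary safety analysis uses these imputed medication dates. This is a minor correction worth making because it is cheap.

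**What to change.** In the medication rows of SAP Appendix 2:

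1. Compare the stop date after its own imputation, not only a complete stop date, with the study intervention start date. Add that a start is never imputed later than the imputed stop.
2. For the long-acting COPD maintenance therapy that qualifies the participant under inclusion criterion 8, set a year-only start in the dosing year to January 1. Alternatively, count that record as prior, and also as concomitant if it continues on or after Day 1.
3. Leave the Day 1 default for other ongoing records whose start relative to dosing is unknown.

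The cost is a few lines of SAP text and of the medication dataset program, using dates already collected. The minimum fields in Protocol 6.8 include no flag for use before the study. The qualifying record therefore has to be identified from drug name, reason for use, dates and criterion 8. COPD medication begun after treatment ended is also recorded and must not be swept in. A small downside is that a January 1 start may be earlier than the true one, but Appendix 2 already bars imputed dates from duration calculations.
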